14.0 Risks to Participants

14.1 Foreseeable Risks:

The risks of MRI are as follows:

- Projectiles: Objects with magnetic properties can be pulled into the magnet and turn into projectiles. To minimize this risk we ask that subjects remove all metallic items (watches, cell phones, hair pins, etc.) prior to entering the scanner and by controlling access to the scanner.
- Claustrophobia: The scanner is a long narrow tube that may cause some people to feel claustrophobic.
- Hearing Damage: The noise generated by the operation of the scanner during a study is loud enough to cause hearing damage if you do not wear hearing protection. Hearing protection is required and is provided by the investigator.
- Nerve Stimulation: Some people experience localized tingling, twitching, or muscle contractions during MRI scans. This is expected, but if it is uncomfortable, the scan can be stopped immediately.
- Disruption of Devices: Some devices can be damaged by magnetic fields and should not be brought into the scanner room. This includes some implanted devices such as pacemakers, cochlear implants, insulin pumps, nerve stimulators, etc. Participants will be screened thoroughly prior to scanning to ensure that they do not have such implanted devices.
- Heating of Devices: The radiofrequency waves used in MRI can heat conductive materials such as metal implants (screws, plates,

> rods, wires, artificial joints, etc.), certain tattoo inks, certain clothing fabrics, jewelry, medication patches, wigs, etc. Participants will be asked to remove these items if possible. If they cannot be removed they will be asked to provide more information to allow MRI staff to be able to make determination on the safety of proceeding with the scan.

> The approved CMRR screening procedures will be employed prior to scanning. The participant will undergo thorough screening for metal at the time of scheduling and, again, prior to entering the MRI suite. During the scan, the participant will have a squeeze ball to signal a desire to stop the scan and the participant will also be in voice communication with the scanner operator.

The risks of tDCS are as follows:

- This study involves the use of a tDCS device, which is considered to be a safe brain stimulation technique that rarely results in adverse events.
- There is currently no evidence of serious side effects.
- Criteria for discontinuation that may rarely occur are sores at the tDCS administration site, and headaches that temporarily affect comfort / functioning.
- Mild side effects that typically resolve upon discontinuation of tDCS include light itching under the electrode at the beginning of administration, headache, fatigue, and nausea.
- The participant may also choose to discontinue stimulation at any time during the session if experiencing discomfort or side effects.
- No other risks are anticipated. Nonetheless, in order to minimize risks, study staff will be using standards of administration that have been shown to be safe in numerous other studies and across more than 2000 studies (Liebetanz et al., 2009; Nitsche et al., 2007; Poreisz, Boros, Antal, & Paulus, 2007) using tDCS; this includes length of administration, magnitude of the current, size of electrode sponges used, and method of applying stimulation.
- Any unanticipated problems or adverse events will be reported to the IRB

The risks of neurocognitive testing / checklists are as follows:

- Neurocognitive testing can be challenging and tiring. Children will be given ample opportunities for breaks and will be given encouragement to complete tasks to the best of their ability.
- Checklists cover sensitive topics. Participants have the option of skipping items that they are uncomfortable answering.

- 14.2 Reproduction Risks: There are no known risks to fetuses from MRI, but we will take steps to ensure that no pregnancies are exposed to MRI nonetheless. Parents and participants will be told that the participant should not undergo MRI if there is a pregnancy or the possibility of a pregnancy (i.e. sexual intercourse without effective contraception taking place). There are no known risks to fetuses from tDCS, but we will similarly take steps to ensure that no pregnancies are exposed to tDCS.
- 14.3 Risks to Others: Parents who accompany children to the MRI facility (CMRR) will be screened as though they will be entering the MRI suite (even though the plan will be for them to remain in the attached control room). All CMRR procedures will be followed in this regard.

15.0 Potential Benefits to Participants

15.1 Potential Benefits: There are no direct benefits for the participant or family. Rather, the research is expected to benefit the population of individuals with FASD through the knowledge acquired.

16.0 Data Management

- *16.1* Data Analysis Plan: Data analyses will include traditional statistical analyses for group differences in neurocognitive and brain measures with control for confounding variables, multiple comparisons, etc.
- 16.2 Power Analysis: We propose to compare changes in cognition and in brain circuitry between the two intervention arms. With an n=20, alpha 0.05, power of 0.8, we have power to detect an effect size of 0.9.
- *16.3* Data Integrity: Neuroimaging data will be subjected to standard quality control measures (both automated and manual) including measuring and controlling for artefacts. Neurocognitive data will be checked for quality by more than one research staff member.

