1.0 Objectives

- 1.1 Purpose:
 - Aim 1: Characterize the feasibility and tolerability of combined cognitive remediation and tDCS in children ages 10-16 with FASD.
 - Hypothesis 1: Children with FASD will tolerate the procedures and remain in the study with less than 20% dropout over the course of cognitive remediation and tDCS
 - Aim 2: Evaluate the potential additive benefits of tDCS to the base cognitive remediation program.
 - Hypothesis 2: Cognitive remediation with active tDCS vs. sham tDCS will result in greater gains over the courses of treatment.
 - Aim 3: Examine the brain circuitry changes following the intervention.
 - Resting and task fMRI will demonstrate greater change with active compared with sham tDCS.

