3.0 Study Endpoints/Events/Outcomes

3.1 Primary Endpoint/Event/Outcome:

The primary endpoints will be BrainHQ (Posit Science, San Francisco, CA) task performance measures.

- Learning curves derived from repeated sessions of BrainHQ training will serve as the primary endpoints:
 - Scene Crasher; Mind Bender; Juggle Factor; Eye for Detail; and Divided Attention
- *3.2* Secondary Endpoint(s)/Event(s)/Outcome(s):
 - Neurocognitive measures will be administered at baseline and again after completion of training:
 - Subtests from the Delis-Kaplan Executive Functioning System (DKEFS)
 - Delis Rating of Executive Functioning (D-REF)
 - NIH Toolbox measures (Flanker, Dimensional Card Sort Test, Picture Sequence Memory Test, and Oral Symbol Digit Test)
 - Functional Connectivity analysis of resting-state fMRI data
 - o Seed-based functional connectivity measure
 - Graph theoretical analysis of connectivity

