5.0 Procedures Involved

- 5.1 Study Design:
 - The study will be a randomized, double-blind, placebo (sham) controlled trial.
 - Eligible participants will be randomized to treatment or placebo in a 1:1 allocation ratio (n=20 active tDCS, n=20 sham).
 - Randomization will be from a computer procedure for randomization and tracking.
 - All members of the team will be blinded to assignment.
 - A block randomization procedure with variable block sizes will be used to maximize unpredictability of assignment.
- 5.2 Study Procedures:
 - Intervention (active tDCS vs. sham): There will be a total of 6 visits for the study an initial baseline and intervention visit; four

additional intervention visits and one follow-up visit (within one week of the last intervention session)

- Visit 1: Baseline session; three hour visit.
 - a. Obtain consent; conduct safety screen for MRI (15 min)
 - b. Baseline MRI scan (45 min)
 - c. Baseline cognitive testing (60 min)
 - d. First tDCS intervention session (60 min)
 - i. 14 minutes set-up
 - ii. 46 minutes of cognitive training interleaved with two 13 minute blocks of active or sham tDCS (26 minutes total active/sham tDCS)
- Visits 2-5: tDCS intervention sessions; one hour visits.
 - a. 14 minutes set-up
 - b. 46 minutes of cognitive training interleaved with two 13 minute blocks of active or sham tDCS (26 minutes total active/sham tDCS)
- Visit 6: Follow-up; two hour visit. Within one week of the last intervention session
 - a. Obtain consent/screen for MRI (15 min)
 - b. Repeat MRI scan (45 min)
 - c. Repeat cognitive testing (60 min)
- Cognitive Training Description (Brain HQ):
 - 46 total minutes of cognitive training using the BrainHQ software (Posit Science, San Francisco, CA) will be completed by each subject in each intervention session.
 - The BrainHQ software includes a number of brain training games which focus on various aspects of attention, reaction time, memory and executive function.
 - Positive findings using the BrainHQ program have been reported in children with ADHD (Mishra, Merzenich, & Sagar, 2013) as well as adults with traumatic brain injury (Lebowitz, Dams O'Connor, & Cantor, 2012).
 - The BrainHQ program allows for real-time monitoring of subject performance and adjusts the difficulty level of individual tasks accordingly.

- Additionally, it allows for quantitative tracking of subject performance over time both within and across intervention sessions.
- tDCS Description:

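### The pre/post cognitive and imaging measures are to be compared as changes between arms with no named model; section 16.1 should specify ANCOVA on the baseline value that the protocol already collects.

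*Combined protocol and SAP*

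**What the plan says.** Section 16.2 (Power Analysis) sets out the comparison as "We propose to compare changes in cognition and in brain circuitry between the two intervention arms" and continues: "With an n=20, alpha 0.05, power of 0.8, we have power to detect an effect size of 0.9". Aim 3 in section 1.1 uses the same framing for imaging: "Resting and task fMRI will demonstrate greater change with active compared with sham tDCS".

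The analysis plan in section 16.1 is a single sentence promising "traditional statistical analyses for group differences in neurocognitive and brain measures with control for confounding variables, multiple comparisons, etc". It names no model and does not mention the baseline score as a covariate. Section 5.2 refers the imaging analysis to published connectivity approaches, but gives no model for comparing the arms before and after the intervention. ANCOVA, a mixed model and baseline adjustment appear nowhere in the document.

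The baseline values are nevertheless part of the design. Section 3.2 states: "Neurocognitive measures will be administered at baseline and again after completion of training". The visit schedule in section 5.2 places an MRI scan and an hour of cognitive testing in visit 1, ahead of the first stimulation session, and repeats both at visit 6. The fMRI, resting and reversal-learning, is collected before and after the intervention.

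**The concern.** A two-group comparison of raw change scores is the natural reading of section 16.2, and it is the analysis that reproduces the 0.9. It fixes the coefficient on the baseline value at 1. ANCOVA estimates that coefficient, and so removes at least as much variance apart from a small finite-sample cost. With 20 per arm, precision limits what Aims 2 and 3 can show on these measures, and the means of improving it are already being collected.

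The open promise in section 16.1 to control for confounders adds a second risk. In a randomised trial of 40, covariates could be chosen after chance imbalances have been seen. Naming the baseline value of the same measure in advance closes that choice.

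The point covers only the pre/post measures in section 3.2 and the reversal-learning fMRI in section 5.2. The primary BrainHQ learning curves are repeated-session data and need a model of their own.

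**Working it through.** **Inputs from the documents.** 20 per arm, 1:1 (section 5.1); alpha 0.05, power 0.8, effect size 0.9 (section 16.2).

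**Assumptions, not in the documents.** Two-sided test; one scalar outcome; bivariate normal baseline and follow-up values with the same SDs and correlation in both arms; pre-post correlation r; ratio k of post SD to pre SD (pre SD set to 1). Section 16.2 does not say which SD the 0.9 refers to. It is read first as SD of change, then as outcome SD.

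**Step 1: reproduce the plan's figure.** The normal approximation gives (1.960 + 0.842) × √(2/20) = 0.886. The noncentral t with 38 df gives 80% power at 0.909, and 79.2% power at 0.9. The stated 0.9 is therefore the figure for an unadjusted two-group comparison with 20 per arm.

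**Step 2: compare the variances.**
- Change score: 1 + k² − 2rk
- ANCOVA residual: k²(1 − r²)
- Difference: 1 − 2rk + r²k² = (1 − rk)²

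The difference is never negative and is zero only when rk = 1. In large samples the unadjusted change comparison therefore cannot be the more precise one.

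**Step 3: power with 20 per arm.** The raw effect is 0.9 × √(1 + k² − 2rk) and the ANCOVA residual SD is k√(1 − r²). ANCOVA has 37 df. Its variance is inflated by 1 + F/38, with F distributed as F(1, 38), for chance baseline imbalance, and power is averaged over F.

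Example, r = 0.5 and k = 1: the SD of change is √(2 − 1) = 1, the raw effect is 0.90, the residual SD is √0.75 = 0.866, and the standardised effect is 0.90/0.866 = 1.04. Power is 88.4%, against 79.2% for change.

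ANCOVA power (%), where unadjusted change gives 79.2% in every cell:

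| k | r = 0.3 | r = 0.5 | r = 0.7 | r = 0.9 |
|---|---|---|---|---|
| 0.8 | 97.1 | 95.1 | 93.2 | 93.9 |
| 0.9 | 94.8 | 91.7 | 88.4 | 85.9 |
| 1.0 | 92.4 | 88.4 | 84.3 | 80.1 |
| 1.1 | 90.0 | 85.6 | 81.3 | 78.1 |
| 1.2 | 87.9 | 83.4 | 79.4 | 79.0 |

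Simulation with 200,000 trials per cell agrees to within about 0.1 point.

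The cells do not describe one clinical scenario. Holding the effect at 0.9 SD of change means that, at k = 1, the raw effect is 1.06, 0.90, 0.70 and 0.40 outcome SD at r = 0.3, 0.5, 0.7 and 0.9.

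**Step 4: find where ANCOVA loses.** It falls behind for r above 0.94 (k = 1.0), between 0.81 and 0.96 (k = 1.1), between 0.71 and 0.91 (k = 1.2) and between 0.64 and 0.86 (k = 1.3), and at no r for k = 0.8 or 0.9. The worst case is rk = 1, where its power is 78.07%: a loss of 1.14 points, with a detectable effect of 0.922 against 0.909. A grid of k from 0.5 to 2 and r from 0 to 0.99 found nothing larger.

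**Step 5: read 0.9 as outcome SD instead (k = 1).**

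| r | Change (%) | ANCOVA (%) |
|---|---|---|
| 0.3 | 65.0 | 81.8 |
| 0.5 | 79.2 | 88.4 |
| 0.7 | 94.7 | 96.9 |
| 0.8 | 99.2 | 99.5 |

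Any multiplicity control applied under section 16.1 would lower all of these figures.

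**The case against.** The strongest reply is that the plan is under-specified and not wrong. Comparing changes is compatible with baseline adjustment, since ANCOVA on the follow-up value and change adjusted for baseline give the same treatment estimate, and controlling for confounders could be stretched to include the baseline score. On that view 79.2% is the power of one reading and not a loss to which the plan is committed. This stands in part: the text does not exclude ANCOVA. But it does not specify it either, and the only analysis that the plan states and powers is the unadjusted comparison.

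The size of the gain also depends on r and k, which the documents do not give. That stands. In parts of the table the gain is slight: 0.9 points at r = 0.9 and k = 1.0, and 0.2 points at r = 0.7 and k = 1.2. In a few cells it is negative. The direction in large samples and the cap on the loss do not depend on r or k.

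The scope is limited too. This is a feasibility pilot, and the primary endpoints are not touched. The calculation applies to scalar outcomes, so it does not carry over to imaging analyses that do not reduce to one number per scan. These limits are accepted. Finally, a repeated-measures model that constrains the baseline means to be equal would serve equally well, so the essential request is baseline adjustment named in advance.

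**Conclusion.** The concern holds. The plan frames the pre/post comparison as unadjusted change, names no model, and leaves unused a baseline value that it collects for each of these outcomes. The 0.9 in section 16.2 is correct as an approximate, unadjusted figure.

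The choice is lopsided. If the effect is 0.9 SD of change, ANCOVA gains up to 17.9 points within the table (97.1 − 79.2, at r = 0.3 and k = 0.8) and can lose at most 1.14 points at any r and k. On the outcome-SD reading with equal SDs, the gain runs from 16.8 points at r = 0.3 (81.8 − 65.0) to 0.3 points at r = 0.8 (99.5 − 99.2). All of this assumes scalar, roughly normal outcomes, 20 completers per arm, a two-sided 0.05 test and no multiplicity adjustment. The practical gain in this trial is unknown until r and k are known. It is an efficiency and pre-specification point that should be acted on, but it does not invalidate the design.

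**What to change.** Add to section 16.1 that each visit 6 cognitive outcome, and each scalar imaging outcome, will be compared between arms by ANCOVA with terms for arm and for the same measure at baseline (equivalently, change adjusted for baseline), and that no covariate will be selected because of observed baseline imbalance. In section 16.2, keep the 0.9 and label it as an unadjusted figure.

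The cost is one sentence in 16.1 and a label in 16.2, with no additional participants, visits or measurements. The statistical price is one degree of freedom plus the effect of chance baseline imbalance: at most 1.14 points of power at a true effect of 0.9 SD of change with 20 per arm.

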17.0 Confidentiality

17.1 Data Security: Data will be handled by trained research staff members. Paper records will be stored in locked file drawers and electronic data storage will meet University security requirements (password protection, encryption, controlled access, audit trails of access, etc.). Protected Health Information will be separated from research data. Research data will be coded and, thus, de-identified. De-identified data will be stored in a local HIPAA-compliant RedCap database managed by the University of Minnesota. Signed consent forms will be scanned into the OnCore system as required by the University. Research information will not be placed into the individual's electronic medical record.

18.0 Provisions to Monitor the Data to Ensure the Safety of Participants

N/A - The principal investigator will monitor safety and data quality for this study. They will ensure that adverse events are reported accordingly and that data are generated, documented (recorded), and reported - in compliance with this protocol, with Good Clinical Practice, and any other applicable regulatory requirements.

19.0 Provisions to Protect the Privacy Interests of Participants

- 19.1 Protecting Privacy: Potential participants will not be contacted to inquire about research participation if they have opted out of research as part of signing the standard UMMC/Fairview consent to treatment form. During telephone screening, potential participants will be given multiple opportunities to decline screening and participation in research. During the study itself, participants will be informed that they are free to skip questions on questionnaires or decline to answer interview questions if they find the material too sensitive or uncomfortable. [name], a licensed clinical psychologist, has worked extensively with patients, families, and research participants over the years and is acutely aware of handling sensitive topics in relation to child mental health and development. He will ensure that all aspects of the study include the consideration of participant comfort and privacy as a top priority.
- 19.2 Access to Participants: As part of the consenting process, participants will give their formal consent for the study team to collect sensitive information. This will include the signing of a separate HIPAA form granting the study team access to the participant's medical record.

20.0 Compensation for Research-Related Injury

- 20.1 Compensation for Research-Related Injury: Compensation for Research-Related Injury: In the event that this research study results in an injury, we will provide treatment including first aid, emergency care, and follow-up as needed. Care for injuries would be billed in the ordinary manner and costs would not be covered by the research study itself.
- 20.2 Contract Language: N/A

21.0 Consent Process

- 21.1 Consent Process (when consent will be obtained):
 - The informed consent process will begin at the time of the telephone screening and will continue throughout participation. During screening, parents will be informed about the purpose of the research, why their child was chosen for possible participation, what the

> potential procedures are, and how long they will take, and payment. This will allow them time to formulate questions which could be posed to investigators at the time of the in-person enrollment visit.

- Enrollment will be done in person with the parent(s) providing consent and the child providing assent.
- 21.2 Waiver or Alteration of Consent Process (when consent will not be obtained): We are requesting a waiver of documentation of the consent for only the phone screen portion of the study. Participants would be consented prior to any other study activities. We need to collect sensitive information from the parent/guardian prior to the first visit and documented consent process in order to determine basic eligibility. All parents will be read the attached script and asked to verbally consent to the phone screen only.
- 21.3 Non-English Speaking Participants: Participants will be English speaking.
- 21.4 Participants Who Are Not Yet Adults (infants, children, teenagers under 18 years of age):
 - The participants in this study will be minors (<18 years of age) at the time of enrollment. Parental consent (from one parent) and child assent will be utilized in all cases at enrollment.
 - Because this is an intervention, foster children and/or wards of the State will not be enrolled.
 - Assent will be obtained from all participants; Assent will be documented with a signed form.

21.5 Cognitively Impaired Adults, or adults with fluctuating or diminished capacity to consent: NA

22.0 Setting

22.1 Research Sites:

- Participants will be recruited from the Fetal Alcohol Spectrum Disorders clinic and the International Adoption Clinic at the University of Minnesota.
- Procedures will be performed in the Center for Neurobehavioral Development (CNBD) and the Center for Magnetic Resonance Research (CMRR).

23.0 Multi-Site Research

N/A; single site only

24.0 Resources Available

24.1 Prior studies by our research group, including a previous study with very similar methodology to this one, have demonstrated high interest on the part of

families in participation. Recruitment targets have been met for all previous studies.

24.2 The principal investigator, [name], will devote approximately 15% effort to the study over the course of the project.

24.3 Facilities include the CMRR (which is ideally set up for neuroimaging work), the CNBD (which is ideally set up for collecting neuropsychological and behavioral data), and the DCRU (which is ideally set up for assisting with biological samples.

24.4 [name], the principal investigator, is a licensed clinical neuropsychologist with 19 years of experience in managing children and adolescents with developmental disorders and mental health conditions. He has conducted numerous studies in the Academic Health Center and knows how to access resources relevant to clinical research as well as for managing unexpected events.

24.5 [name] will personally ensure that research coordinators are appropriately trained and overseen. [name] (Psychiatry) has a Clinical Research Specialist ([name]) as well as a Regulatory Specialist ([name]) who are available to assist with training and oversight.

